10.2 Responsibility for Analyses/In-house Blinding

The statistical analysis of the data obtained from this study will be the responsibility of the Clinical Biostatistics department of the Sponsor.

The Sponsor will generate the randomized allocation schedule(s) for study treatment assignment. Randomization will be implemented in IVRS/IWRS.

This study will be conducted as a double-blind study under in-house blinding procedures. The official, final database will not be unblinded until medical/scientific review has been performed, protocol deviations have been identified, and data have been declared final and complete. In addition, blinded independent central imaging review will be performed on imaging scans without knowledge of the treatment group assignments of participants.

Planned interim analyses are described in Section 10.7. Blinding to treatment assignment will be maintained at all investigational sites. The results of interim analyses will not be shared with the investigators prior to the completion of the study. Participant-level unblinding will be restricted to an external unblinded statistician and external unblinded scientific programmer performing the interim analysis, who will have no other responsibilities associated with the study.

Treatment-level results of the interim analysis will be provided by the unblinded statistician to the external data monitoring committee (eDMC). Limited additional Sponsor personnel may be unblinded to the treatment-level results of the interim analysis (analyses), if required, in order to act on the recommendations of the eDMC. The extent to which individuals are unblinded with respect to results of interim analyses will be documented by the unblinded statistician.

The eDMC will serve as the primary reviewer of the unblinded results of the DFS and OS at interim analyses and will make recommendations for discontinuation of the study or modification to an EOC of the Sponsor. Depending on the recommendations of the eDMC, the Sponsor may prepare a regulatory submission. If the eDMC recommends modifications to the design of the protocol or discontinuation of the study, the EOC may be unblinded to results at the treatment level in order to evaluate and direct the Sponsor protocol team as to the appropriate actions to be taken on these recommendations. Additional logistical details, revisions to the above plan, and data monitoring guidance will be provided in the DMC Charter.

Prior to final study unblinding, the unblinded statistician and unblinded scientific programmer will not be involved in any discussions regarding modifications to the protocol, statistical methods, identification of protocol deviations, or data validation efforts after the interim analyses.

10.3 Hypotheses/Estimation

Objectives and hypotheses of the study are stated in Section 4.

10.4 Analysis Endpoints

10.4.1 Efficacy Endpoints

10.4.1.1 Primary

Disease-Free Survival

DFS, as assessed by the investigator, is defined as the time from randomization to the first documented local recurrence, or occurrence of distant kidney cancer metastasis(es), or death due to any cause, whichever occurs first. See Section 10.6.1 for the censoring rules.

10.4.1.2 Secondary

Overall Survival

OS is defined as the time from randomization to death due to any cause. Participants without documented death at the time of the final analysis will be censored at the date of the last follow-up.

Disease Recurrence-Specific Survival

- DRSS1 is defined as the time from randomization to the first documented local recurrence of RCC as assessed by the investigator.
- DRSS2 is defined as the time from randomization to the first documented local recurrence with visceral lesion or occurrence of distant kidney cancer metastasis(es) with visceral lesion, whichever occurs first, as assessed by the investigator.

Event-Free Survival

EFS is to be assessed by BICR. EFS is defined as time from randomization to the first documented local recurrence or occurrence of distant kidney cancer metastasis(es) among participants, which by BICR were considered disease-free at baseline (M0/M1 NED); or disease progression among participants, which by BICR were considered to have baseline disease (M1), or death due to any cause, whichever occurs first. See Section 9.2.1 for the definition of disease progression.

10.4.2 Safety Endpoints

Safety endpoints are described in Section 5.4.1.2.

10.5 Analysis Population

10.5.1 Efficacy Analysis Population

The Intention-to-Treat population will serve as the population for the primary and key secondary efficacy analyses. All randomized participants will be included in this population. Participants will be analyzed in the treatment group to which they are randomized.

10.5.2 Safety Analysis Population

The All Participants as Treated (APaT) population will be used for the analysis of safety data in this study. The APaT population consists of all randomized participants who received at least 1 dose of study treatment. Participants will be analyzed in the treatment group corresponding to the study treatment they actually received for the analysis of safety data using the APaT population. For most participants this will be the treatment group to which they are randomized. Participants who take incorrect study treatment for the entire treatment period will be included in the treatment group corresponding to the study treatment actually received. Any participant who receives the incorrect study treatment for one cycle, but receives the correct treatment for all other cycles will be analyzed according to the correct treatment group and a narrative will be provided for any events that occur during the cycle for which the participant is incorrectly dosed.

At least 1 laboratory measurement obtained subsequent to at least 1 dose of study treatment is required for inclusion in the analysis of each specific parameter. To assess change from baseline, a baseline measurement is also required.

10.6 Statistical Methods

10.6.1 Statistical Methods for Efficacy Analyses

This section describes the statistical methods that address the primary and secondary objectives on OS and disease recurrence-specific survival. Methods related to the secondary objective, PROs, as well as exploratory objectives will be described in the sSAP.

Efficacy results that will be deemed to be statistically significant after consideration of the Type I error control strategy are described in Section 10.8 – Multiplicity. Nominal p values may be computed for other efficacy analyses, but should be interpreted with caution due to potential issues of multiplicity.

10.6.1.1 Disease-Free Survival

The nonparametric Kaplan-Meier method will be used to estimate the DFS curve in each treatment group. The hypotheses addressing a treatment difference in DFS will be tested by the stratified log-rank test. A stratified Cox proportional hazard model with Efron's method of tie handling will be used to estimate the magnitude of the treatment difference (ie, hazard ratio [HR]) between the treatment arms. The HR and its 95% CI from the stratified Cox model with Efron's method of tie handling and with a single treatment covariate will be reported. The stratification factors used for randomization (see Section 7.3.1) will be applied to both the stratified log-rank test and the stratified Cox model.

Since participants enrolled with baseline disease by BICR could have a different time to event distribution compared to participants who were disease-free at baseline by BICR, a sensitivity analysis will be performed using the stratified Cox model and stratified log-rank test with stratification factors used for randomization with baseline disease status by BICR as an additional stratum.

Since disease recurrence is assessed periodically, disease recurrence can occur any time in the time interval between the last assessment when disease recurrence was not documented and the assessment when disease recurrence is documented. For the primary analysis, for the participants who have disease recurrence (local recurrence or occurrence of distant kidney cancer metastasis(es)) as assessed by the investigator’s review, the true date of disease recurrence will be approximated by the date of the first assessment at which disease recurrence is objectively documented, regardless of discontinuation of study treatment. Death is always considered as a confirmed disease recurrence event.

In order to evaluate the robustness of the DFS endpoint, a sensitivity analysis with a different set of censoring rules may be performed. The sensitivity analysis is the same as the primary analysis except that events after 2 consecutive missed disease assessments or after new anticancer therapy, if any, should be censored at last disease assessment prior to the earlier date of ≥ 2 consecutive missed disease assessments and new anticancer therapy.

The censoring rules for primary and sensitivity analysis are summarized in [Table 10](#).

Table 10 Censoring Rules for Primary and Sensitivity Analysis of Disease-Free Survival

Situation	Primary Analysis	Sensitivity Analysis
No recurrence and no death; new anticancer treatment is not initiated	Censored at last disease assessment	Censored at last disease assessment
No recurrence and no death; new anticancer treatment is initiated	Censored at last disease assessment	Censored at last disease assessment before new anticancer treatment
Recurrence or death documented after ≤ 1 missed disease assessment and before new anticancer treatment, if any	Event at date of documented recurrence or death	Event at date of documented recurrence or death
Recurrence or death documented immediately after ≥ 2 consecutive missed disease assessments, or after new anticancer treatment, if any	Event at date of documented recurrence or death	Censored at the last disease assessment prior to the earlier date of ≥ 2 consecutive missed disease assessments and new anticancer treatment, if any

The proportional hazards assumption on DFS will be examined using both graphical and analytical methods if warranted. The log [-log] of the survival function versus time for DFS will be plotted for the comparison between pembrolizumab and the placebo arm. If the curves are not parallel, indicating that hazards are not proportional, supportive analyses may be conducted to account for the possible nonproportional hazards effect associated with immunotherapies: for example, using the Restricted Mean Survival Time method [Uno, H., et al 2014] and parametric method [Odell, P. M., et al 1994]. Further details of sensitivity analyses will be described in the sSAP.

10.6.1.2 Overall Survival

The nonparametric Kaplan-Meier method will be used to estimate the survival curves. The hypotheses of treatment difference in survival will be tested by the stratified log -rank test.

A stratified Cox proportional hazard model with Efron's method of tie handling will be used to estimate the magnitude of the treatment difference (ie, the HR). The HR and its 95% CI from the stratified Cox model with a single treatment covariate will be reported. The stratification factors used for randomization will be applied to both the stratified log-rank test and the stratified Cox model.

The OS analysis will be conducted according to the hypothesis testing plan as described in Section 10.7 and Section 10.8.

10.6.1.3 Disease Recurrence-Specific Survival

The nonparametric cumulative incidence estimator will be used to estimate the DRSS1 and DRSS2 curves in each treatment group. For DRSS1, only local recurrence is counted as an event. Death, or occurrence of distant kidney cancer metastasis(es) will be censored at documented date of disease metastasis or death, whichever occurs first. For DRSS2, only disease recurrence with visceral lesion is counted as an event. Death, local recurrence without visceral lesion, distant metastasis without visceral lesion will be censored at documented date of disease recurrence or death, whichever occurs first.

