10.6.1.4 Event-Free Survival

The nonparametric Kaplan-Meier method will be used to estimate the EFS curve in each treatment group. Although no formal hypothesis will be performed for testing the treatment difference in EFS, nominal p-value from stratified log-rank test will be provided to serve as a sensitivity analysis for the primary endpoint of DFS by investigator. A stratified Cox proportional hazard model with Efron's method of tie handling will be used to estimate the magnitude of the treatment difference (ie, hazard ratio [HR]) between the treatment arms. The HR and its 95% CI from the stratified Cox model with Efron's method of tie handling and with a single treatment covariate will be reported. The stratification factors used for randomization (see Section 7.3.1) with baseline disease status by BICR as an additional stratum will be applied to both the stratified log-rank test and the stratified Cox model.

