10.9 Sample Size and Power Calculations

The study will randomize participants in a 1:1 ratio into the pembrolizumab and placebo arms. DFS and OS are the primary endpoint and key secondary endpoint, respectively. The sample size was planned for 950, but the following power calculations are based on 990, which is a number more in line with the actual final number of randomized participants.

For the DFS endpoint, based on a target number of 332 events and one IA at approximately 80% of the target number of events, the study has approximately 95% power to detect a HR of 0.67 at an overall alpha level of 2.5% (1-sided).

For the OS endpoint, the power is conditional on the null hypothesis of DFS being rejected, based on a target number of 200 events and 3 interim analyses at approximately 47%, 66%, and 86% of the target number of events, the study has approximately 79% power to detect a HR of 0.67 or approximately 88% power to detect a HR of 0.635 at an overall alpha level of 2.5% (1-sided).

The above sample size and power calculations for DFS and OS assume the following:

- DFS follow a Poisson mixture cure rate model [de Castro, M., et al 2010] with assumed cure rate of 0.3. The cure rate of 0.3 is estimated based on historical data [Leibovich, B. C., et al 2003].
- The median DFS is assumed to be 45 months for those not cured in the control group.
- OS follows an exponential distribution with a median of 145 months for the control group.
- Enrollment period of 27 months with monthly accrual of 20 participants during the first 5 months and monthly accrual of 30 participants from month 6 to month 21, and monthly accrual of 1 participant for the last month.
- A yearly drop-out rate of 2% for DFS and 1% for OS.

Technical details on the Poisson mixture cure rate model are in Appendix 7. The sample size and power calculation were performed using R (package “gsDesign”).

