12.7 Appendix 7: Poisson Mixture Model

The Poisson mixture model is applied to account for the failure rates decreasing over time in a trial in which the patient population is a mixture of participants who are susceptible to disease recurrence and participants who would not have a disease recurrence event after long-term follow-up. The latter participants are called long-term survivors. The Poisson mixture model assumes a survival function [de Castro, M., et al 2010] for a control group (c) as a function of time (t), as follows:

[figure not shown]
$$S(t) = \exp(-\theta(1 - \exp(-\lambda t)))$$

where $\theta = -\log(\text{Cure_Rate})$, λ is a constant hazard rate, and $t \geq 0$.

In the adjuvant setting, according to the published literature [Leibovich, B. C., et al 2003] and study assumptions, ~30% participants will be long-term survivors or will be cured in the long-term (ie, Cure_Rate=0.3), and it is more likely that after approximately 5 to 6 years after study initiation there will be minimal accumulation of DFS events.

According to the published literature [Leibovich, B. C., et al 2003], it is assumed that DFS follows a Poisson mixture model distribution with median DFS of 45 months in the placebo group. Figure 3 below shows the DFS curves using the Poisson mixture model and exponential model. Compared to the curve from the exponential model, the curve from the Poisson mixture model looks more similar to the curve in the published literature.

Figure 3 Disease-Free Survival Curves Using the Poisson Mixture Model and Exponential Model

Supplemental Statistical Analysis Plan (sSAP)

TABLE OF CONTENTS

TABLE OF CONTENTS.....	2
LIST OF TABLES.....	4
LIST OF FIGURES	5
1. INTRODUCTION	6
2. SUMMARY OF CHANGES.....	6
3. ANALYTICAL AND METHODOLOGICAL DETAILS.....	9
3.1 STATISTICAL ANALYSIS PLAN SUMMARY	9
3.2 RESPONSIBILITY FOR ANALYSES/IN-HOUSE BLINDING	10
3.3 HYPOTHESES/ESTIMATION	11
3.4 ANALYSIS ENDPOINTS	13
3.4.1 Efficacy Endpoints.....	13
3.4.1.1 Primary.....	13
3.4.1.2 Secondary.....	13
3.4.2 Safety Endpoints	14
3.4.3 Patient Reported Outcome (PRO) Endpoints	14
3.4.3.1 Secondary.....	14
3.4.3.2 Exploratory	14
3.5 ANALYSIS POPULATIONS	15
3.5.1 Efficacy Analysis Populations.....	15
3.5.2 Safety Analysis Populations	15
3.5.3 PRO Analysis Population	16
3.6 STATISTICAL METHODS.....	16
3.6.1 Statistical Methods for Efficacy Analyses.....	16
3.6.1.1 Disease-Free Survival (DFS).....	16
3.6.1.2 Overall Survival (OS)	18

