3.6.1.3 Disease Recurrence Specific Survival

The non-parametric cumulative incidence estimator will be used to estimate the DRSS1 and DRSS2 curves in each treatment group. For DRSS1, only local recurrence is counted as an event. Death, or occurrence of distant kidney cancer metastasis(es) will be censored at documented date of disease metastasis or death, whichever occurs first. For DRSS2, only disease recurrence with visceral lesion is counted as an event. Death, local recurrence without visceral lesion, distant metastasis without visceral lesion will be censored at documented date of disease recurrence or death, whichever occurs first.

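### DRSS1 and DRSS2: the plan names a cumulative incidence estimator but censors the competing events, so coded as written it is 1 minus Kaplan-Meier and overstates recurrence risk in each arm

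*Combined protocol and SAP*

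**What the plan says.** Protocol section 10.6.1.3 gives the estimator first: "The nonparametric cumulative incidence estimator will be used to estimate the DRSS1 and DRSS2 curves in each treatment group". It then sets the event rule, "For DRSS1, only local recurrence is counted as an event", and the handling of everything else: "Death, or occurrence of distant kidney cancer metastasis(es) will be censored at documented date of disease metastasis or death, whichever occurs first". The DRSS2 rule has the same form.

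The sSAP, section 3.6.1.3, repeats both parts: "The non-parametric cumulative incidence estimator will be used to estimate the DRSS1 and DRSS2 curves in each treatment group", and for DRSS2 "Death, local recurrence without visceral lesion, distant metastasis without visceral lesion will be censored at documented date of disease recurrence or death".

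Neither section mentions competing risks or a competing-event code, and neither specifies a test or a hazard ratio for DRSS. The other time-to-event endpoints (DFS, OS, EFS) are assigned Kaplan-Meier; for EFS, section 10.6.1.4 says "The nonparametric Kaplan-Meier method will be used to estimate the EFS curve in each treatment group". In the objectives (protocol section 4), DRSS is an other secondary endpoint, worded as a comparison between arms.

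**The concern.** A cumulative incidence estimator differs from 1 minus Kaplan-Meier only if competing events stay in the data as competing events. Naming it for DRSS alone suggests that a competing-risks analysis was intended, but the censoring sentences remove what it needs. Two competent programmers could therefore produce different curves from the same text.

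Censoring treats a participant who has died, or who has already had another type of recurrence, as still able to have the event later at the same rate as those remaining at risk. Death rules that out. A distant metastasis does not rule out a later local recurrence biologically, but required imaging generally ends at the first recurrence (protocol section 9.2.1.3), so a later one is generally not observed. What the data can support is the probability of local recurrence as the first event.

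At stake are the absolute risks of local and visceral recurrence read from these curves, which are the only DRSS analysis the plan specifies.

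**Working it through.** The plan states no event count, rate or power for DRSS, so there is no DRSS figure to reproduce.

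**Direction, without assumptions.** Let H₁ be the cumulative hazard of the event of interest, S₁ the Kaplan-Meier curve for that event with all others censored, and S the curve for all first events together.
- With competing events (Aalen-Johansen): F(t) = ∫ S(u−) dH₁(u).
- As written: 1 − S₁(t) = ∫ S₁(u−) dH₁(u).

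Competing events make S smaller than S₁, so the as-written curve is the higher one in each arm. A simulation with 200,000 participants (month 48, 20% share) gave 10.3% with competing events, 13.48% after recoding them as censored, and 13.48% for 1 minus Kaplan-Meier.

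**Size, illustrative.** Inputs from the documents:
- Control curve S(t) = exp(−θ(1 − exp(−λt))) with cure rate 0.3, so θ = −ln 0.3 = 1.204 (protocol Appendix 7).
- DFS hazard ratio 0.67 (protocol section 10.9).
- A 45-month median, which the documents read in two ways. Appendix 7: "it is assumed that DFS follows a Poisson mixture model distribution with median DFS of 45 months in the placebo group". Section 10.9: "The median DFS is assumed to be 45 months for those not cured in the control group". Both are carried through.

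Assumed: the event of interest is a constant share p of the DFS hazard, and 0.67 applies to every event type.

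Solving for λ:
- Overall median: S(45) = 0.50 gives λ = 0.01905, S(36) = 0.550, S(50) = 0.477.
- Median among the not cured: S(45) = 0.3 + 0.7 × 0.5 = 0.65 gives λ = 0.00984, S(36) = 0.698, S(50) = 0.626.

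Under these assumptions the competing-event risk is p(1 − S) and the as-written risk is 1 − S^p. The pembrolizumab arm uses S^0.67 in place of S. Example (p = 0.2, month 36, overall median): 0.2 × (1 − 0.550) = 9.0%, against 1 − 0.550^0.2 = 11.3%.

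| Share p | Month | Median reading | Placebo risk: competing vs as written | Arm difference (points): competing vs as written |
|---|---|---|---|---|
| 20% | 36 | overall | 9.0% vs 11.3% | 2.4 vs 3.6 |
| 20% | 36 | not cured | 6.0% vs 6.9% | 1.8 vs 2.2 |
| 20% | 50 | overall | 10.5% vs 13.7% | 2.6 vs 4.3 |
| 20% | 50 | not cured | 7.5% vs 8.9% | 2.1 vs 2.9 |
| 80% | 36 | overall | 36.0% vs 38.0% | ratio 1.10 |
| 80% | 36 | not cured | 24.1% vs 25.0% | ratio 1.06 |

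Over shares of 10% to 80%, months 36 to 50 and both readings, placebo risk is overstated by 3% to 36% in relative terms, and the arm difference is multiplied by 1.06 to 1.74. The top of both ranges comes from a 10% share at month 50 (overall median), where absolute amounts are small: 5.2% vs 7.1% in placebo, and a difference of 1.3 vs 2.3 points.

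**Coherence check.** At month 50 (overall median), two complementary event types with shares of 20% and 80% have as-written risks of 13.7% + 44.7% = 58.4%. The true total is 1 − 0.477 = 52.3%. The as-written risks cannot both be probabilities of a first event.

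**When the arm difference would not be inflated.** With 0.67 on the event of interest, inflation of the difference stops at a competing-event hazard ratio of 1.32 to 1.69 (shares 10% to 80%, months 36 to 60, both readings). Pembrolizumab would have to raise the competing hazard by that much.

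**Against sampling error.** I refer to 1,500 simulated trials with 495 per arm, uniform accrual over 27 months, 2% yearly drop-out, a cut at month 50, p = 0.2 and the overall median. At month 36 the mean placebo estimate was 9.0% (SD 1.35 points) with competing events and 11.3% as written. The difference was 2.4 points (SD 1.8) against 3.6.

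**The case against.** The strongest reply is that the text is ambiguous rather than wrong. The estimator is named, and censored may loosely mean only that follow-up for the endpoint stops and no event is counted. An analyst who follows the estimator name and codes competing events gets the right curve. That is true. But the tables just after use the word literally (protocol Table 10 for DFS, Table 11 for OS), and the sSAP, which exists to add analysis detail, repeats the conflict. Nothing in the documents tells a programmer to depart from the stated rule.

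A second reply is that DRSS1 is defined as time to first documented local recurrence, not local recurrence as the first event, so metastasis need not compete. The imaging rule answers this for what can be observed, and death competes on any reading.

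The points on size partly stand. The shares and the common hazard ratio are assumptions. The inflation of the arm difference in the simulation, 3.6 − 2.4 = 1.2 points, is below its SD of 1.8. Under the not-cured reading the placebo bias at month 36, 6.9 − 6.0 = 0.9 points, is below a rough binomial standard error of 1.1, from √(0.06 × 0.94 / 495). The arm risk ratio moves only modestly: at a 20% share, month 50 and overall median, it is 0.75 with competing events and 0.69 as written. This limits the importance of the error but does not remove it.

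Censoring competing events is proper for a cause-specific hazard ratio, but none is planned for DRSS.

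**Conclusion.** The concern holds. Followed literally, the stated censoring rule turns the named estimator into 1 minus Kaplan-Meier and overstates the risk in each arm whenever competing events occur. That direction needs no assumption about event shares. The size does: the effect is material for DRSS1 if local recurrence is a minority of first events, and small for DRSS2 if most events are visceral (3% to 7% relative at an 80% share, months 36 to 50). Inflation of the arm difference also depends on the assumed hazard ratios.

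This should be corrected, but it does not threaten the trial's main conclusions. DRSS lies outside the alpha-controlled tests, and DFS, OS, alpha and power are unaffected.

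**What to change.** In protocol section 10.6.1.3 and sSAP section 3.6.1.3:
- Replace the instruction to censor with a statement that death and the other recurrence types are treated as competing events at their documented dates.
- Name the Aalen-Johansen estimator.
- State that only participants with no recurrence and no death are censored, at last disease assessment.
- State how a participant whose local and distant recurrence are documented at the same assessment is classified, since DRSS1 then needs a rule.
- Optionally, because the objective is comparative, add a descriptive stratified cause-specific hazard ratio with its confidence interval. Censoring competing events is appropriate there.

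The cost is a few words in the DRSS1 and DRSS2 sentences of each document, plus the classification rule. Standard software suffices and no new data are needed.
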